- Incidence of medications with possible antiviral activity (hydroxychloroquine, lopinavir/ritonavir, ribavirin or remdesivir) or adjunctive therapy use (e.g., tocilizumab)
- Incidence (and length in days) of extracorporeal membrane oxygenation use
- Incidence (and length in days) of renal replacement therapy use
- Intolerance of high dose (50mg) losartan after tolerating 25mg
- Change in SARS-CoV-2 viral load determined by quantitative PCR

Inclusion criteria:

1. Age ≥ 18 years admitted to the University of Kansas Health System.
2. Confirmation of infection with SARS-CoV-2 by PCR testing.
3. Hypoxic respiratory failure
 - Requiring mechanical ventilation or oxygen OR a SpO₂ $\leq 94\%$ on room air or a P_aO₂/F_iO₂ (P/F) ratio <300 OR tachypnea (respiratory rate ≥ 24 breaths/min).
4. Other concomitant medications such as antivirals and hydroxychloroquine are allowed.
5. Participants prescribed standard of care (SOC) losartan (25mg QD) within 48 hours of consenting may be considered for enrollment if eligibility criteria are met based on EMR data assessment, i.e. no other ARB or ACE prior to SOC medication administration. If participant is eligible and signs consent form, investigational losartan 25mg QD will be ordered to replace SOC prescription on the following scheduled dose.

Exclusion criteria:

1. Pregnancy.
2. Respiratory failure due to a process other than COVID-19.
3. Intolerance to ARBs.
4. Previous treatment with an ARB or ACE inhibitor (see exception in inclusion criteria).
5. Current chronic use of medication with known interactions with losartan including NSAIDs (intermittent prior use is acceptable), potassium supplementation aliskiren.
6. Blood pressure less than 90 mm Hg systolic or 60 mm Hg diastolic recorded on at least two readings 30 min apart.
7. Need for vasopressors, unless norepinephrine ≤ 0.1 μ g/kg/min
8. Hyperkalemia (serum K⁺ > 5.5 mM).
9. Known cardiac failure (left ventricular ejection fraction $\leq 35\%$), renal insufficiency (Cockcroft-Gault < 30 mL/min/1.73 m² or urinary output < 20 mL/h), hepatic failure (LFTs > 5 x normal upper limit).
10. Known renal artery stenosis.
11. Neurological, psychiatric, endocrine or neoplastic diseases that are judged to interfere with participation in the study.
12. On another interventional trial (including one for COVID-19) that excludes participation.
13. Meeting all inclusion criteria for more than 48 hours prior to Day 0

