- Monitor subject for safety and losartan stoppage criteria.
- For participants following inclusion criteria #5: Day 0 assessments should be performed on enrollment day as well as day 1 **or** day 2 based on first dose of SOC losartan administration.

Day 3:

- Dose escalation: On study day 3 if none of the parameters listed below are met the dose of losartan will be increased to 50 mg once daily.

Day 4 until study completion:

- Monitor subject for safety and losartan stoppage criteria.
- Treatment group will have nasopharyngeal swab and research plasma collected at end of study.

Stoppage criteria for losartan

- Hyperkalemia (persistent values >5.5 mM recorded on at least 2 readings).
- Worsening renal function (Cockcroft-Gault <30 mL/min/1.73 m²) or urinary output <20 mL/h.
- Skin rashes, palpitations or other moderate or severe adverse events (interference with usual daily activities) without clear explanation should warrant immediate cessation of treatment and notification of study personnel.
- Development of sustained hypotension defined as SBP <90 mmHg, DBP <60 mmHg recorded on at least two readings 30 min apart or use of norepinephrine >0.1 µg/kg/min.

[figure not shown]
- Any change in monitor lab parameters deemed significant and potentially related to study drug by the Investigator.

Dose de-escalation criteria

- Any change in monitoring parameter after dose increase from 25 mg to 50 mg that is considered significant by the investigator will trigger a decrease dose back to 25 mg
- If abnormal parameter is resolved and, in the opinion of the investigator, is unlikely to be related to losartan will increase dose back to 50 mg
- If de-escalation criteria is met after re challenging 50mg dose, the dose will be once more decreased to 25mg until the end of the study.

Criteria for resuming after stopping

- If stoppage criteria have resolved and reason for stoppage is felt to be unlikely or possibly related to losartan, discussion of resumption of losartan with medical monitor
- Dose resumption will start at 25 mg. If stopped at 25 mg → the dose will be continued for three days followed by increase to 50 mg if tolerated. If stopped at 50 mg, 25 mg will be started and escalated to 50 mg the day after if tolerated.

Control

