Hemoglobin	Hemoglobin (Hgb) <LLN - 10.0 g/dL; <LLN - 6.2 mmol/L; <LLN - 100 g/L Follow up	Hgb <10.0 - 8.0 g/dL; <6.2 - 4.9 mmol/L; <100 - 80g/L ; follow up	Hgb <8.0 - 6.5 g/dL; <4.9 - 4.0 mmol/L; <80 - 65 g/L; transfusion indicated; stop losartan, follow up	Life-threatening consequences; urgent intervention indicated; stop losartan	Death
Leukocytes	<LLN - 3000/mm3; <LLN - 3.0 x 10e9 /L; follow closely	<3000 - 2000/mm3; <3.0 - 2.0 x 10e9 /L; stop losartan; follow up	<2000 - 1000/mm3; <2.0 - 1.0 x 10e9 /L; stop losartan; follow up and further investigation	<1000/mm3; <1.0 x 10e9 /L; stop losartan; follow up and further investigation	
Platelets	<LLN - 75,000/mm3; <LLN - 75.0 x 10e9 /L; follow closely	<75,000 - 50,000/mm3; <75.0 - 50.0 x 10e9 /L; follow closely, stop losartan	<50,000 - 25,000/mm3; <50.0 - 25.0 x 10e9 /L; follow closely, stop losartan,	<25,000/mm3; <25.0 x 10e9 /L; follow closely, stop losartan, transfer to ICU	
Angioedema	N/A	N/A	Angioedema occurs – mild: stop losartan, transfer to ICU	Angioedema occurs – severe tongue swelling: stop losartan, transfer to ICU	Death
Hypotension (for participants in ICU on sedation for mechanical ventilation ONLY)	Initiation of vasopressors	Increase in vasopressor dose to >0.1; stop losartan, follow up	Persistent hypotension without alternative cause; stop losartan, follow up	Irreversible end organ damage related to hypotension; stop losartan, follow up	Death
Hypotension (for participants NOT in ICU on sedation for mechanical ventilation)	Asymptomatic, intervention not indicated	Non-urgent medical intervention indicated; stop losartan, follow up	Urgent medical intervention or transfer to ICU indicated; stop losartan, follow up	Life-threatening and urgent intervention indicated; losartan, follow up	Death

Creatinine	>1 - 1.5 x baseline; >ULN - 1.5 x ULN; follow up	>1.5 - 3.0 x baseline; >1.5 - 3.0 x ULN; close follow up	>3.0 baseline; >3.0 - 6.0 x ULN; stop losartan, nephrology intervention	>6.0 x ULN; stop losartan, nephrology intervention	
Potassium&	>ULN to 5.5 mmol/L; monitor	>5.5 - 6.0 mmol/L; stop losartan, close follow up	>6.0 - 7.0 mmol/L; urgent intervention indicated, stop losartan, intervention	>7.0 mmol/L; life-threatening consequences; stop losartan, intervention	

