AST, ALT, alkaline phosphatase	>ULN - 3.0 x ULN; monitor closely	Asymptomatic with AST, ALT, alk.P. >3.0 - 5.0 x ULN; >3 x ULN with the appearance of worsening of fatigue, nausea, vomiting, right upper quadrant pain or tenderness, fever, rash, or eosinophilia or bilirubin elevation; stop losartan, monitor	>5.0 - 20.0 x ULN; >5 x ULN for >2 weeks; stop losartan, monitor	>20.0 x ULN; stop losartan, monitor, other interventions	
CPK#	>ULN - 2.5 x ULN; monitor closely	>2.5 x ULN - 5 x ULN; stop losartan, monitor closely	>5 x ULN - 10 x ULN; stop losartan, monitor closely	>10 x ULN; stop losartan, monitor closely, possible admission with other abnormalities	

& Given that hyperkalemia occurs with patients on Losartan and there could be patients with renal dysfunction that falls just under the 1.5 mmol/L creatinine exclusion point, the DMC would recommend a modification to the reporting of abnormal results of serum potassium. We suggest that upon receipt of a level greater than 5.5 mM, the blood draw be repeated within 24 hours and that the PI for the study respond to the repeat level by either reassuring the patient that all is well or if the level is still rising discontinuing the study drug. Since there will be blood draws frequently during this study, we feel that continuing the study subject on study drug if the level returned to normal on repeat testing is safe, especially in the expected monitored setting.

Only done when clinically indicated

Pregnancy

Female subjects will be tested for pregnancy by hospital policy. If pregnant they will be excluded.

It is not expected that a female subject becomes pregnant while participating in the study. In the rare case this does occur, study drug must be stopped immediately and permanently discontinued. Losartan does not have effects on a fetus in the 1st trimester but could later on. The investigator must notify the DSMB and IRB within 24 hours of the site's knowledge of the subject's pregnancy and other agencies as by law. Pregnancy itself does not constitute an AE. Pregnancy test will be performed at all site visits.

Data monitoring plan will be implemented as follows:

- Safety monitoring will be done:
 - All SAEs attributable to study drug will be reported to the study investigator(s) and discussed with an internal safety and monitoring group of 5 experts consisting of an intensivist(s), infectious disease specialist(s), ethicist and biostatistician. These experts may not report to the PI directly.

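### Patients can enter with liver or blood-count values at which Table 1 already says to stop losartan, and the adverse-event definition has no new-or-worsened rule

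*Combined protocol and SAP*

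**What the plan says.** All references are to the combined protocol and SAP.

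- **Entry.** Exclusion criteria, item 9, bars "hepatic failure (LFTs > 5 x normal upper limit". No exclusion sets a limit for leukocytes, platelets, hemoglobin or CPK.
- **Table 1.** The Grade 2 liver cell begins "Asymptomatic with AST, ALT, alk.P. >3.0 - 5.0 x ULN", adds a symptomatic alternative (">3 x ULN with the appearance of worsening of fatigue" and other signs), and ends by telling staff to stop losartan and monitor. Grade 1 asks only for close monitoring. The leukocyte row gives its stop at Grade 2: "<3000 - 2000/mm3; <3.0 - 2.0 x 10e9 /L; stop losartan; follow up". Platelets carry a stop from below 75,000/mm3, hemoglobin from below 8.0 g/dL, and CPK from above 2.5 x ULN.
- **Stoppage criteria for losartan.** Some laboratory stops are absolute, such as "Hyperkalemia (persistent values >5.5 mM recorded on at least 2 readings" and a Cockcroft-Gault limit of 30. For other laboratory values the clause is "Any change in monitor lab parameters deemed significant and potentially related to study drug by the Investigator".
- **Day 3.** The rule is that "if none of the parameters listed below are met the dose of losartan will be increased to 50 mg once daily".
- **Criteria for resuming after stopping.** Resumption is considered "If stoppage criteria have resolved and reason for stoppage is felt to be unlikely or possibly related to losartan".
- **Definition of an Adverse Event.** Table 1 safety data and the stoppage criteria count as adverse events, collected from signature of the consent form. Sample size and Statistics then compares total AEs and SAEs with controls, using a 20% margin.

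**The concern.** A patient with a stable, symptom-free ALT of 4 x ULN passes exclusion 9 and starts 25 mg. Table 1 says to stop at that value. The stoppage list names no liver limit and, for laboratory values without one, requires a change, which this patient has not had. Two clinicians following the protocol could reasonably do opposite things. If Table 1 governs and the resumption rule covers its stops, a value that stays where it was at entry keeps the patient off drug, and the recorded stop says nothing about losartan.

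The second issue is counting. No sentence says a Table 1 value must be new or worse than at entry, so a literal reader would log the entry value as an adverse event. These rows matter because blood dyscrasias and hepatitis are among the rare serious losartan effects the protocol names. The total of AEs and SAEs is the only stated safety criterion.

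**Working it through.** **1. Entry limit against Table 1 stop level**

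| Table 1 row | First stop level | Entry limit | Eligible at stop level? |
|---|---|---|---|
| AST/ALT/alk. phosphatase | >3.0 x ULN | excluded only >5 x ULN | yes, >3.0 to 5.0 |
| Leukocytes | <3000/mm3 | none | yes |
| Platelets | <75,000/mm3 | none | yes |
| Hemoglobin | <8.0 g/dL | none | yes |
| CPK | >2.5 x ULN | none | yes, if measured |
| Potassium | >5.5 | excluded >5.5 | no |
| Creatinine | >3.0 x baseline or ULN | set through Cockcroft-Gault <30 | not counted |

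Count: 4 of 7 laboratory rows, or 5 of 7 with CPK. CPK is conditional because the Table 1 note says it is done only when clinically indicated, although Parameters to be collected lists creatine kinase throughout.

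Point check on the liver row (eligible if not >5; stop if >3): 3.0 x ULN is eligible with no stop; 3.1, 4.0 and 5.0 are eligible and at a stop; 5.1 is excluded.

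**2. Where the plan does align the limits**

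The exclusion and stoppage lists use the same figure for five parameters: potassium 5.5, Cockcroft-Gault 30, urine output 20 mL/h, blood pressure 90/60 and norepinephrine 0.1. The creatinine row in Table 1 also has a baseline comparator; the liver and blood-count rows have none. Nothing suggests the mismatch is deliberate.

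**3. Scale for the liver row (assumption, not an estimate)**

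The documents do not give the share q of enrolled patients with liver values >3 to 5 x ULN at Day 0. I take 1% to 10%. With n = 50 treated, the expected number is 50q and the chance of at least one is 1 - (1 - q)^50.

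| q | Expected of 50 | Chance of at least one |
|---|---|---|
| 1% | 0.5 | 39.5% |
| 2% | 1.0 | 63.6% |
| 5% | 2.5 | 92.3% |
| 10% | 5.0 | 99.5% |

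**4. Effect on the safety comparison**

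This depends on how the total is measured, which the plan does not state.

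- *Events per patient, absolute difference:* equal entry events in both groups cancel.
- *Proportion with any event:* if a share q in both groups has an entry value, independent of later events, a true 20-point difference becomes 20(1 - q): 19.8 points at q = 1% and 18.0 at q = 10%.
- *Weight of one patient on that scale:* with 50 treated and 50 x 2 = 100 controls, a treated patient whose only event is an entry value moves the difference by 1/50 = 2 points, and such a control by 1/100 = 1 point.

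**The case against.** The best defence is that the text allows a coherent reading. The first column of Table 1 is headed as adverse events, those are occurrences during the study collected from consent, and the general laboratory stop speaks of a change. On that reading a stable pre-consent value is neither an event nor a stop. This is a fair reading for counting. For dosing it has to be supplied by the reader, because Table 1 ties its action to the value itself. Investigator judgement, the medical monitor and safety reviews after 5 and 25 patients would soften the effect, but none of them says which instruction governs.

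The stoppage list also covers moderate adverse events, and Grade 2 is defined as moderate. That might link the two lists, but the clause is qualified by interference with daily activities, which symptom-free ALT does not cause.

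Three stronger readings are tempting and are not supported:

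- *The stoppage list acts on laboratory values only when they change.* It does not: the potassium and Cockcroft-Gault stops are absolute. The gap is confined to liver values, blood counts and CPK.
- *Such a patient would be escalated to 50 mg on Day 3.* This is one reading. The parameters listed below most naturally means the stoppage list that follows, but Table 1 is also below.
- *Controls with exclusion criteria would inflate the control event rate.* Such controls are a fallback under Control, they would need to have those abnormalities, and entry values would have to be counted. Events missed in control charts would act the other way.

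**Conclusion.** The point holds in a limited form. Exclusion 9 and Table 1 give opposite dosing instructions for an eligible patient with a stable liver value of >3 to 5 x ULN, and the three blood-count rows have the same gap (CPK too, if measured). This rests on direct comparison of stated limits and on reading the stop at the end of the Grade 2 liver cell as applying to the whole cell, as the action does in other rows.

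The adverse-event definition has no explicit new-or-worsened rule, so on a literal reading entry values can enter the comparison of total AEs and SAEs. A reader might infer that the comparison is therefore biased, or diluted. The documents do not support that: dilution depends on an unstated choice of measure, entry frequencies are not given, and neither size nor direction can be computed. The figures for q between 1% and 10% show scale only. The change is worth making because the dosing conflict is real and cheap to remove.

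**What to change.** **1. Exclusion criteria.** Exclude patients whose last value before the first dose is at a Table 1 stop level: AST, ALT or alkaline phosphatase >3 x ULN, leukocytes <3000/mm3, platelets <75,000/mm3, hemoglobin <8.0 g/dL, and CPK >2.5 x ULN if measured. Leave the Table 1 stops and the potassium repeat-test footnote as they are. This is preferable to waiving Grade 2 stops for entry values, which would loosen a safety rule. It would also blunt the symptomatic liver criterion: a patient entering at 4 x ULN who then develops symptoms is still Grade 2.

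**2. Definition of an Adverse Event.** Count a Table 1 value or stoppage criterion only if it is new, or at least one grade worse, relative to the last value before consent and first study dose. For retrospective controls, who sign no consent form, use the value when all inclusion criteria are first met. The rule is still needed after the first change, because Grade 1 entry values remain eligible and are also in Table 1.

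**Cost.** One exclusion line and two sentences. Blood counts and liver enzymes are already on the list of parameters to be collected, and control values come from the health record. Some patients lose eligibility; on the assumed 1% to 10%, the liver row alone would account for 0.5 to 5 of every 50 otherwise eligible. Worsening within one grade, such as ALT from 1.1 to 2.9 x ULN, would not be counted as an adverse event.

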Thus, good evidence suggests that at least acute treatment with ARBs could ameliorate lung injury in COVID-19. We therefore propose to test losartan in a Phase I proof of concept and safety trial. The primary hypothesis to be tested is that losartan treatment is safe in the setting of acute SARS-CoV-2 infection. Secondarily, losartan can potentially reduce the length of respiratory failure due to SARS-CoV-2.

Significance

Importance of the problem: As outlined above, there is currently no data that supports specific treatment options for respiratory failure in COVID-19. There are active or soon to be active clinical trials that may show promise in this space such as blocking IL-6 with tocilizumab²⁰ or using hydroxychloroquine. None of these therapies are without side effects and alternative or additional approaches could lessen the burden of respiratory failure in this patient population.

Approach and Protocol

This is an open label, phase 1 clinical trial to evaluate the safety of losartan in respiratory failure due to COVID-19.

Clinical Trial setup:

Detailed inclusion and exclusion criteria are listed below. Briefly, 50 patients with COVID-19 and respiratory failure who meet criteria and agree to participation in the study will be placed on losartan 25 mg daily on study day 0. If parameters are met the dose of losartan will be increased to 50 mg on study day 3. Participants will continue losartan until they experience resolution of respiratory failure (normal oxygen levels on room air), are discharged from the hospital, meet stoppage criteria (detailed below) or complete 14 days of therapy.

Primary hypothesis and endpoint:

- Losartan is safe in acute respiratory failure due to SARS-CoV-2.

Secondary endpoints:

- Losartan reduces the number of days on supplemental oxygen in respiratory failure due to COVID-19
- Incidence of mechanical ventilation use
- Days on mechanical ventilation
- Incidence of non-invasive positive pressure ventilation or heated high flow nasal cannula use
- Days on non-invasive positive pressure ventilation or high flow nasal cannula
- Incidence of transfer to ICU from non-ICU hospital bed
- ICU length of stay (days)
- In-hospital mortality
- Hospital length of stay (days)
- Cumulative incidence of severe adverse events
- Cumulative incidence of adverse events
- Change from baseline in oxygenation

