Since there is no information on the effects of losartan in human beings suffering from COVID-19, a statistical analysis based on efficacy is not possible. From a safety perspective, we would accept considering losartan equivalent or superior to the comparison group not receiving losartan (historical or no consent) if there is a $\pm 20\%$ difference in total AE/SAEs. Historical controls will be matched with study participants based on upon age, sex and disease severity in a 2:1 ratio for safety comparison. From a safety perspective, losartan's long track record as a safe medication is reassuring. See section on DSMB for further details on safety monitoring and analysis.

Confidentiality

All information provided by the subject to the investigators, and all information that is collected about the subjects by the investigators, shall be kept confidential to the extent that is provided by law. Computer data files will be stored and backup up to secure, HIPPA compliant, password protected computers and servers. Electronic data capture into REDCap system will be used. Access to these databases will be restricted to individuals associated with the study who require access to the data to perform their duties. These individuals will be named by the principal investigator prior to initiation of the clinical trial. The subject's actual identity cannot be ascertained exclusively from these data and the subject's name shall not be used in any publications. All investigators and staff involved in the research protocol will be bound by this agreement of confidentiality.

Adverse Event and Serious Adverse Event Documentation

Definition of an Adverse Event

For the purpose of this protocol, an AE will be defined as any untoward medical occurrence in a subject during the study listed under DMSB - Anticipated Adverse Events and Grading Scale section of this protocol as well as safety monitoring data listed on table 1 as well as stoppage criteria for losartan.

The event does not necessarily have a causal relationship with the treatment. AEs will be collected for both study groups, treatment and control from the time the ICF is signed until the subject completes study participation.

Definition of a Serious Adverse Event

An SAE is any AE that meets any of the following outcomes:

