- Fatal (death, regardless of cause, that occurs during participation in the study or occurs after participation in the study and is suspected of being a delayed toxicity due to administration of the study drug)
- Life-threatening, such that the subject was at immediate risk of death from the reaction as it occurred
- Inpatient hospitalization or prolongation of hospitalization

- Persistent or significant disability/incapacity (disability is defined as a substantial disruption of a person's ability to conduct normal life functions)
- Congenital anomaly or birth defect
- Important medical event that, based upon appropriate medical judgment, may jeopardize the subject or may require medical or surgical intervention to prevent 1 of the outcomes listed above (e.g., an allergic bronchospasm requiring intensive treatment)

Data Safety and Monitoring Plan and Internal DSMB

Anticipated Adverse Events and Grading Scale

Losartan side effects: The most common side effects are fatigue and dizziness. Serious adverse events that are rare include angioedema, hypotension, renal dysfunction or failure, blood dyscrasias, hepatitis, or rhabdomyolysis (clinical assessment of muscle pain). Skin rashes, palpitations or other moderate or severe adverse events without other clear explanation warrants immediate cessation of treatment and notification of study personnel, who will take appropriate reporting actions.

Grading Scale

Grade 1:

Mild; asymptomatic or mild symptoms; clinical or diagnostic observations only; intervention not indicated.

Grade 2

Moderate; minimal, local or noninvasive intervention indicated; limiting age-appropriate instrumental ADL*Grade 3

Severe or medically significant but not immediately life-threatening; hospitalization or prolongation of hospitalization indicated; disabling; limiting self care ADL**.

Grade 4

Life-threatening consequences; urgent intervention indicated.

Grade 5

Death related to AE.

Activities of Daily Living (ADL)

* Instrumental ADL refer to preparing meals, shopping for groceries or clothes, using the telephone, managing money, etc.

** Self-care ADL refer to bathing, dressing and undressing, feeding self, using the toilet, taking medications, and not bedridden.

Table 1

Adverse event	Grade 1	Grade 2	Grade 3	Grade 4	Grade 5

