 - Any serious AE or SAE attributable to study drug will be shared with the medical monitor and safety and monitoring group within 24 hrs. The members will make the decision whether or not to stop the trial.
- All SAEs will be reported to the safety and monitoring group and the appropriate agencies including FDA and IRB as required.
- All adverse effects will be reported according to the rules to the FDA, the IRB and our internal DMSB
- Initial interim analysis on safety will be done after the first 5 patients and reviewed by the internal DSMB.
- The DSMB may stop the study due to safety or futility.
- All DSMB reports will be shared with the IRB.

Safety Reporting

Data monitoring plans will be implemented as follows: The study will be closely monitored by the PI and Co-PIs. Any relevant AE or SAE will be reported to the medical monitor and to the DSMB (separate charter).

- DSMB meeting will occur after the first 5 patients, 25 patients and at end of study, or more frequently if needed.
 - Safety monitoring will be done by the DSMB. Safety monitoring will be done as follows: The investigators will continuously monitor the study for side effects. If any AE or serious adverse events (SAEs) occur, the physicians will assess the event and report them to the appropriate authorities if needed as per Good Clinical Practice. Subjects might be withdrawn from the study if they experience intolerance to the study medication, initially based on the investigators' discretion.
 - All adverse effects will be discussed among the investigators
 - If deemed severe the data will be shared with the medical monitor and the safety and monitoring group. The group will make the decision whether or not to stop the trial based on safety data.
- All SAEs will be reported to the IRB and the appropriate agencies including FDA as required.

- All adverse effects will be reported according to the rules to the FDA (if needed), the IRB and the DSMB.

Safety Reviews

Safety review will occur at least every month and/or if a SAE occurs. The internal safety and monitoring group will meet after the first 5 patients, 25 patients and at end of study or more frequently if needed. If needed, the biostatics core will assist in data analysis for adverse events as well (fee for service basis). However, this is a small study.

Removal of Subjects from Study

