A subject withdrawal is defined as a discontinuation from the study for any reason. Subjects may withdraw or be withdrawn from this study for the following reasons:

- At their own request or at the request of their authorized representative at any time for any reason
- If, in the investigator's opinion, continuation in the study would be detrimental to the subject's well-being

Subjects must be withdrawn from the study for the following reasons:

- Subjects with an occurrence of any medical condition which, either because of its severity or duration or necessary change in treatment, contravenes the condition of the study or puts the patient at unnecessary risk or harm.
- Subjects with an occurrence of an AE/SAE, which in the opinion of the investigator and/or subject requires termination of treatment
- Subjects who are noncompliant with the protocol per the investigator's discretion
- Pregnancy

In all cases, the reason for withdrawal will be recorded in the subject's medical records and case report forms. Subjects who terminate the clinical study prematurely, either at their own request or on the recommendation of the clinical investigator, will be considered early terminations. Subjects who withdraw from the study will not be replaced but asked that their progress off drug can be followed as well. The DSMB should be notified of all early withdrawals and/or termination in the trial.

REGULATORY CONSIDERATIONS

The protocol will be submitted to the KUMC IRB. The study was registered on clinicaltrials.gov.

ADMINISTRATIVE SECTION

Protocol Amendments

Any amendments to the protocol will be approved by the PI and co-investigators and the independent Data Monitoring Committee and the DSMB. All amendments will be submitted to the IRBs for review and approval prior to implementation unless the amendment details changes related to safety.

Protocol Deviations

The investigator will only make changes to the protocol procedures when necessary to protect the safety, rights, and welfare of the subjects. In such an event where protocol procedures are changed, the investigators are responsible for notifying the IRBs and the internal DSMB.

In the event that an isolated, unforeseen instance occurs resulting in a protocol deviation, the investigators are to document this deviation and notify IRBs as by the rules at KUMC.

Case Report Form (CRF)

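### An AE that ends losartan also requires withdrawal from the study, and the plan does not say that later events in those patients are collected or counted, so the safety comparison may lean towards safe

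*Combined protocol and SAP*

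**What the plan says.** The primary hypothesis is "Losartan is safe in acute respiratory failure due to SARS-CoV-2". Sample size and Statistics tests it by comparing total AE/SAEs with controls, allowing a difference of ±20%.

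Four provisions decide which events reach that comparison:

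- **Removal of Subjects from Study** defines withdrawal as leaving the study, not as stopping the drug. Under "Subjects must be withdrawn from the study for the following reasons" it lists "Subjects with an occurrence of an AE/SAE, which in the opinion of the investigator and/or subject requires termination of treatment".
- **Definition of an Adverse Event** sets the window: "AEs will be collected for both study groups, treatment and control from the time the ICF is signed until the subject completes study participation".
- **Removal of Subjects from Study**, on what happens next: "Subjects who withdraw from the study will not be replaced but asked that their progress off drug can be followed as well". The length, the content and the use of that follow-up are not given.
- **Definition of a Serious Adverse Event** counts any death during participation. A later death counts only if it "occurs after participation in the study and is suspected of being a delayed toxicity due to administration of the study drug".

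Other sections point towards patients staying in the study after a drug stop. Criteria for resuming after stopping lets losartan restart in some cases. Table 1 pairs many drug stops with follow-up or monitoring. Safety Reporting uses a softer verb: "Subjects might be withdrawn from the study if they experience intolerance to the study medication".

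**The concern.** The plan ties leaving the study to the outcome that the study is meant to measure. A losartan patient with harm serious enough to end treatment must, on the wording, leave the study, and nothing guarantees that what happens next is counted. The measure is a total of events, so shortened observation lowers it directly.

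The trigger can act only on patients who take losartan. For consenting controls, the Day 0 procedures provide for data collection to the end of the study. Retrospective controls are read from the health record without consent (section Control). Events lost by this route therefore come from the losartan side alone, and the loss makes losartan look safer in the study's primary comparison.

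**Working it through.** **No plan figure to reproduce.** The protocol gives no AE rate, discontinuation rate, alpha or power. The argument rests on the text, and the arithmetic only shows what the gap could amount to.

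**Text, step by step**

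1. An AE is judged to require an end to treatment. The rule then demands withdrawal from the study.
2. The AE window closes when participation is complete. Leaving the study is naturally read as the end of participation, although the protocol does not say so expressly.
3. After that, follow-up is requested, and no section places its findings in the ±20% comparison.
4. The one stated extension is a death suspected to be delayed drug toxicity. A death attributed to COVID-19 after withdrawal is not covered.
5. Data monitoring plan and Safety Reporting require all SAEs to be reported, but neither changes the collection window.

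**Illustration**

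Share of losartan-arm events lost = d·m·r·(1 − t/14) / [(1 − d) + d·m]

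All four inputs are assumptions:

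- d: share of losartan patients withdrawn for an AE, 10–30%
- t: day of withdrawal, 3–7
- m: event rate in those patients relative to the others, 1–3
- r: share of them not followed afterwards, 25–100%

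The 14 days is the protocol's maximum treatment duration, used here as an assumed AE window. A constant event rate over that window is also assumed.

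| Case | d | t | m | r | Calculation | Lost |
|---|---|---|---|---|---|---|
| Low | 0.10 | 7 | 1 | 0.25 | 0.0125 / 1.0 | about 1% |
| Mid | 0.20 | 5 | 2 | 0.50 | 0.1286 / 1.2 | 10.7% |
| High | 0.30 | 3 | 3 | 1.00 | 0.7071 / 1.6 | 44.2% |

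In the mid case, with control events fully captured, a true event ratio of 1.20 would be seen as 1.20 × (1 − 0.107) = 1.07. A true ratio of 1.34 would be seen as 1.20, since 1.20 / 0.893 = 1.34.

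If no withdrawn patient is followed (r = 1) and withdrawal falls on day 4, the loss is:

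- 7.1% (d = 0.10, m = 1)
- 14.3% (d = 0.20, m = 1)
- 23.8% (d = 0.20, m = 2)
- 33.0% (d = 0.30, m = 2)

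Following half of these patients halves each figure. If all stay under collection (r = 0), the loss by this route is zero.

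**The case against.** The strongest reply is that the protocol does not treat every drug stop as an exit. Meeting stoppage criteria is listed in Clinical Trial setup beside recovery, discharge and 14 days of therapy as one way that losartan ends. Resumption after discussion with the medical monitor presupposes a patient still in the study, and Table 1 repeatedly asks for follow-up. This stands as a limit. A reader might infer that, say, a fall in renal function that meets a stoppage criterion leads automatically to withdrawal, and the documents do not support that. The mandatory rule applies where the AE is judged to require an end to treatment. Resumption is open only when the cause is thought unlikely or possibly related to losartan, so stops judged more strongly related have no described route back and are the most exposed.

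Other stronger readings also go too far:

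- **AE collection certainly closes.** This is the natural reading, but it is not spelled out, and some withdrawn patients will agree to follow-up. Events are at risk of loss, not known to be lost.
- **A fresh permission is needed.** The consent form is not in the material reviewed and may already cover chart data after a drug stop.
- **Controls contribute every event.** For retrospective controls the protocol mentions only medical information on safety criteria, with no start or end of observation. Complete capture is not shown.
- **In-hospital mortality and length of stay are cut short.** These follow the hospital stay, and nothing ties them to the AE window.
- **Safety Reporting flatly contradicts the mandatory rule.** It concerns intolerance at the investigators' discretion, and the mandatory trigger also rests on opinion. The passages need reconciling, but the conflict is partial.

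**Conclusion.** The concern holds as a risk of one-sided loss. The plan requires study withdrawal for a treatment-ending AE, does not secure collection afterwards, and does not say that off-drug events count. None of the softer passages keeps collection open for a patient withdrawn under the mandatory rule.

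Losses by this route can only lower the losartan total, so their direction is towards safe whatever inputs are assumed. Their size is not known: about 1% to 44% of losartan-arm events, mid case near 11%, all on assumed inputs. The net bias also depends on how completely control events are captured, which the plan leaves open.

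A reader might infer that the loss is about as large as the ±20% margin. That is not established. The mid case is smaller, and the protocol does not say whether the margin is relative or absolute, or whether it counts events or patients. Because the triggering AE is recorded, a count of patients with at least one AE would lose little by this route, although later SAEs and deaths could still be missed.

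**What to change.** 1. In Removal of Subjects from Study, separate discontinuation of losartan from withdrawal from the study. End data collection only when consent to data collection is withdrawn.
2. In Definition of an Adverse Event, collect AEs, SAEs, deaths of any cause and the secondary outcomes from the chart over one common window in treated patients and all controls, whether or not losartan was stopped. Day 14, or discharge if earlier, is one example of such a window.
3. State in Sample size and Statistics that events after a drug stop count in the safety comparison.
4. Confirm that the consent form covers this collection.
5. Reconcile Stoppage criteria, Criteria for resuming, Table 1, Safety Reporting and Removal of Subjects on what a drug stop means for study participation. No clinical stopping rule needs to change for this.

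The cost is protocol wording, possibly consent wording, and some extra chart abstraction for inpatients. The losartan AE count may look less favourable.
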